#### 5.1.6 Adverse Events Associated with Pembrolizumab

The most common adverse reactions (reported in  $\geq 20\%$  of patients in clinical trials of pembrolizumab) included fatigue, cough, nausea, pruritus, rash, decreased appetite, constipation, arthralgia, and diarrhea. The following warnings are associated with the use of pembrolizumab:

##### Immune-Mediated Pneumonitis

Pneumonitis occurred in  $\sim 3\%$  of melanoma patients treated in clinical trials of pembrolizumab. The median time to development of pneumonitis was 5 months with a median duration of 4.9 months. The one patient with Grade 3 pneumonitis required initial treatment with high-dose systemic corticosteroids (greater than or equal to 40 mg prednisone or equivalent per day) followed by a corticosteroid taper. Pneumonitis completely resolved in seven of the nine patients with Grade 2-3 pneumonitis.

##### Immune-Mediated Colitis

Colitis (including microscopic colitis) occurred 1% of melanoma patients treated in clinical trials of pembrolizumab. The median time to onset of was 6.5 months with a median duration of 2.6 months. All three patients with Grade 2 or 3 colitis were treated with high-dose corticosteroids (greater than or equal to 40 mg prednisone or equivalent per day).

##### Immune-Mediated Hepatitis

Hepatitis (including autoimmune hepatitis) occurred in 0.5% of melanoma patients treated in clinical trials of pembrolizumab. The time to onset was 22 days for the case of Grade 4 hepatitis, which lasted 1.1 months. The patient with Grade 4 hepatitis permanently discontinued pembrolizumab and was treated with high-dose (greater than or equal to 40 mg prednisone or equivalent per day) systemic

corticosteroids followed by a corticosteroid taper. Both patients with hepatitis experienced complete resolution of the event.

#### Immune-Mediated Hypophysitis

Hypophysitis occurred in 0.5% of melanoma patients treated in clinical trials of pembrolizumab. The time to onset was 1.7 months for the patient with Grade 4 hypophysitis and 1.3 months for the patient with Grade 2 hypophysitis. Both patients were treated with high-dose (greater than or equal to 40 mg prednisone or equivalent per day) corticosteroids followed by a corticosteroid taper and remained on a physiologic replacement dose.

#### Renal Failure and Immune-Mediated Nephritis

Nephritis occurred in 3 (0.7%) patients of melanoma patients treated in clinical trials of pembrolizumab, consisting of one case of Grade 2 autoimmune nephritis (0.2%) and two cases of interstitial nephritis with renal failure (0.5%), one Grade 3 and one Grade 4. The time to onset of autoimmune nephritis was 11.6 months after the first dose of pembrolizumab (5 months after the last dose) and lasted 3.2 months; this patient did not have a biopsy. Acute interstitial nephritis was confirmed by renal biopsy in two patients with Grades 3-4 renal failure. All three patients fully recovered their renal function with treatment with high-dose corticosteroids (greater than or equal to 40 mg prednisone or equivalent per day) followed by a corticosteroid taper.

#### Immune-Mediated Hyperthyroidism

Hyperthyroidism occurred in 5 (1.2%) of 411 melanoma patients treated in clinical trials of pembrolizumab. The median time to onset was 1.5 months and the median duration was 2.8 months (range 0.9 to 6.1). One of two patients with Grade 2 and the one patient with Grade 3 hyperthyroidism required initial treatment with high-dose corticosteroids (greater than or equal to 40 mg prednisone or equivalent per day) followed by a corticosteroid taper. One patient (0.2%) required permanent discontinuation of pembrolizumab due to hyperthyroidism. All five patients with hyperthyroidism experienced complete resolution of the event.

#### Immune-Mediated Hypothyroidism

Hypothyroidism occurred in 34 (8.3%) of 411 melanoma patients treated in clinical trials of pembrolizumab. The median time to onset of hypothyroidism was 3.5 months. All but two of the patients with hypothyroidism were treated with long-term thyroid hormone replacement therapy. The other two patients only required short-term thyroid hormone replacement therapy. No patient received corticosteroids or discontinued pembrolizumab for management of hypothyroidism. Thyroid disorders can occur at any time during treatment.

#### Other Immune-Mediated Adverse Reactions

Other clinically important immune-mediated adverse reactions can occur. The following clinically significant, immune-mediated adverse reactions occurred in

less than 1% of patients treated with pembrolizumab, including exfoliative dermatitis, uveitis, arthritis, myositis, pancreatitis, hemolytic anemia, partial seizures arising in a patient with inflammatory foci in brain parenchyma, and adrenal insufficiency.

Across clinical studies with pembrolizumab in approximately 2,000 patients, the following additional clinically significant, immune-mediated adverse reactions were reported in less than 1% of patients: myasthenic syndrome, optic neuritis, and rhabdomyolysis.

#### Embryofetal Toxicity

Based on its mechanism of action, pembrolizumab may cause fetal harm when administered to a pregnant woman. Animal models link the PD-1/PD-L1 signaling pathway with maintenance of pregnancy through induction of maternal immune tolerance to fetal tissue.

#### Steven's Johnson Syndrome (SJS) and Toxic Epidermal Necrolysis (TEN)

The risk of SJS and TEN is reported at approximately 0.4 – 7 cases per million patient years in the general adult population. Independent risk factors include certain medications such as anticonvulsants, sulfonamides, aminopenicillins, allopurinol, and NSAIDs. Non-medication triggers include infection, contrast media, and vaccinations. Malignancy is associated with an increased mortality rate in patients with SJS and TEN.

#### Myocarditis

A total of 6 cases of myocarditis have been reported in patients treated with pembrolizumab in clinical trials in an expanded access program. There was one fatal case reported in a clinical trial. Immune-mediated myocarditis should be suspected if other causes of myocarditis such as infection or prior radiation therapy have been excluded. Risk factors include certain medications and treatment modalities such as radiation, anthracycline, alkylating agents and most recently checkpoint inhibitors.

### **5.1.7 Contraception**

Pembrolizumab may have adverse effects on a fetus in utero. Furthermore, it is not known if pembrolizumab has transient adverse effects on the composition of sperm.

For this trial, male subjects will be considered to be of non-reproductive potential if they have azoospermia (whether due to having had a vasectomy or due to an underlying medical condition).

Female subjects will be considered of non-reproductive potential if they are either:

- (1) postmenopausal (defined as at least 12 months with no menses without an alternative medical cause; in women < 45 years of age a high follicle

stimulating hormone (FSH) level in the postmenopausal range may be used to confirm a post-menopausal state in women not using hormonal contraception or hormonal replacement therapy. In the absence of 12 months of amenorrhea, a single FSH measurement is insufficient.);

OR

(2) have had a hysterectomy and/or bilateral oophorectomy, bilateral salpingectomy or bilateral tubal ligation/occlusion, at least 6 weeks prior to screening;

OR

(3) has a congenital or acquired condition that prevents childbearing.

Female and male subjects of reproductive potential must agree to avoid becoming pregnant or impregnating a partner, respectively, while receiving study drug and for 120 days after the last dose of study drug by complying with one of the following:

(1) practice abstinence† from heterosexual activity;

OR

(2) use (or have their partner use) acceptable contraception during heterosexual activity.

Acceptable methods of contraception are‡:

Single method (one of the following is acceptable):

- intrauterine device (IUD)
- vasectomy of a female subject's male partner
- contraceptive rod implanted into the skin

Combination method (requires use of two of the following):

- diaphragm with spermicide (cannot be used in conjunction with cervical cap/spermicide)
  - cervical cap with spermicide (nulliparous women only)
  - contraceptive sponge (nulliparous women only)
  - male condom or female condom (cannot be used together)
  - hormonal contraceptive: oral contraceptive pill (estrogen/progestin pill or progestin-only pill), contraceptive skin patch, vaginal contraceptive ring, or subcutaneous contraceptive injection

†Abstinence (relative to heterosexual activity) can be used as the sole method of contraception if it is consistently employed as the subject's preferred and usual lifestyle and if considered acceptable by local regulatory agencies and ERCs/IRBs. Periodic abstinence (e.g., calendar, ovulation, sympto-thermal, post-ovulation methods, etc.) and withdrawal are not acceptable methods of contraception.

‡ If a contraceptive method listed above is restricted by local regulations/guidelines, then it does not qualify as an acceptable method of contraception for subjects participating at sites in this country/region.

Subjects should be informed that taking the study medication may involve unknown risks to the fetus (unborn baby) if pregnancy were to occur during the study. In order to participate in the study subjects of childbearing potential must adhere to the contraception requirement (described above) before C11-AMT PET imaging is performed starting at the time of consent and continued throughout the study period up to 120 days after the last dose of trial therapy (i.e., pembrolizumab). If there is any question that a subject of childbearing potential will not reliably comply with the requirements for contraception, that subject should not be entered into the study.

#### **5.1.8 Use in Pregnancy**

If a patient inadvertently becomes pregnant while on treatment with pembrolizumab, the patient will immediately be removed from the study. The site will contact the patient at least monthly and document the patient's status until the pregnancy has been completed or terminated. The outcome of the pregnancy will be reported to the Sponsor and to Merck without delay and within 24 hours if the outcome is a serious adverse experience (e.g., death, abortion, congenital anomaly, or other disabling or life-threatening complication to the mother or newborn).

The study investigator will make every effort to obtain permission to follow the outcome of the pregnancy and report the condition of the fetus or newborn to the Sponsor. If a male patient impregnates his female partner, the study personnel at the site must be informed immediately and the pregnancy reported to the Sponsor and to Merck and followed as described above and in Section 7.3.3.

#### **5.1.9 Use in Nursing Women**

It is unknown whether pembrolizumab is excreted in human milk. Since many drugs are excreted in human milk, and because of the potential for serious adverse reactions in the nursing infant, patients who are breast-feeding are not eligible for enrollment.

#### **5.1.10 Overdose**

For purposes of this trial, an overdose of pembrolizumab will be defined as any dose of 1,000 mg or greater ( $\geq 5$  times the indicated dose). No specific information is available on the treatment of overdose of pembrolizumab. Appropriate supportive treatment should be provided if clinically indicated. In the event of overdose, the subject should be observed closely for signs of toxicity. Appropriate supportive treatment should be provided if clinically indicated.

If an adverse event(s) is associated with (“results from”) the overdose of a Merck product, the adverse event(s) is reported as a serious adverse event, even if no other seriousness criteria are met.

If a dose of Merck’s product meeting the protocol definition of overdose is taken without any associated clinical symptoms or abnormal laboratory results, the overdose is reported as a non-serious Event of Clinical Interest (ECI), using the terminology “accidental or intentional overdose without adverse effect.”

All reports of overdose with and without an adverse event must be reported within 24 hours to the Sponsor and within 2 working days hours to Merck Global Safety. (Attn: Worldwide Product Safety; [contact]) (see section 7.3.3.1 )

#### **5.1.11 Risks Associated with C11-AMT PET**

As with any radiotracer, subjects will be exposed to additional radiation above the natural background/cosmic radiation exposure. In particular, the radiation dose following the C11-AMT will be approximately 0.325 rem, which is equivalent to extra 1.1 years of the radiation exposure that everyone receives from annual natural background radiation. In addition, there is at least a theoretical risk of infection after injection of C11-AMT due to bacterial contamination of the product during the process of manufacturing C11-AMT. This is minimized by filtering the product and performing sterility testing prior to injection. Finally, the product may contain impurities other than C11-AMT; these are either byproducts of the chemical reactions used to generate C11-AMT or solvents used during the process to purify C11-AMT. This will be controlled by testing the final product using gas chromatography to ensure chemicals used to clean the reaction vessel have been properly removed. It is possible that up to 5% of ethanol may be present in the final product. Given that the total amount to be injected will be only a few mL, subjects may rarely experience symptoms similar to ingestion of less than a glass of wine.

6.0 EVALUATIONS AND ASSESSMENTS

6.1 Time and Events Table (After screening perform C11-AMT scan and then a research biopsy prior to Cycle 1/Day 1 of pembrolizumab)

Procedure	Screening Period 1 	Pretreatment Period 	D1 Cycle 1 	D1 Cycle 2 	D1 Cycle 3 	D1 Cycle 4 	End of Study Treatment 	Long-term Follow-up 
Informed Consent	X							
Medical History	X 							X
Physical Exam	X 		X 	X 	X 	X 	X 	
ECOG Performance Status	X		X	X	X	X	X	
CBC w/differential	X		X	X	X	X	X	
Hematology 	X		X	X	X	X	X	
INR/PT and PTT	X							
Serum chemistries 	X		X	X	X	X	X	
Liver function tests (LFTs) 	X		X	X	X	X	X	
Thyroid panel 	X				X		X	
Urine or serum pregnancy	X 		X 					
Pembrolizumab IV			X	X	X	X		
Brain MRI 	X 							
FDG PET 	X 						X	
CT scan neck chest, abdomen/pelvis 	X 						X	
AMT PET 		X						
Toxicity evaluations 	X		X	X	X	X	X	X
Fresh tumor biopsy		X						

Concomitant Medications	X		X	X	X	X	X	
Eligibility checklist	X							
Survival documentation								X

### Key to Time and Events Table

The time interval between informed consent and initiation of pembrolizumab consists of a screening period and a pretreatment period and overall it should not exceed 28 days. The screening period starts from informed consent and ends immediately before C11-AMT imaging and biopsy which will be performed at UNC Main Campus. This period of C11-AMT scanning and research biopsy are inclusively called the “pre-treatment period.” During the pre-treatment period, the procedure for fresh biopsy collection will also be performed at UNC. Patients must be deemed eligible prior to entering the pre-treatment period. During the screening period patients will be assessed for eligibility based on history, physical examination, inclusion/exclusion criteria, and blood work. Baseline standard of care radiographic imaging will be performed taking into account timing and type of radiographic imaging prior to study enrollment. Based on the pattern and anatomic location of tumors decisions regarding the bed positions that will be held during the C11-AMT PET imaging session as well as the optimal method and location for fresh biopsy collection are made. Finally, the eligibility will be reviewed by the UNC study coordinator and signed off by the Principal Investigator and Multicenter Project Manager. Submission of source documents will be required at least 4 days before C11-AMT PET imaging is performed. The pre-treatment period starts from the day of C11-AMT PET imaging and ends with initiation of pembrolizumab. It involves assessing the quality of C11-AMT PET imaging with the option to repeat once more if necessary. During the pre-treatment period the procedure for fresh biopsy collection is performed.

Unless otherwise noted, screening evaluations and eligibility packet submissions will be completed at a minimum of 4 days prior to C11-AMT PET imaging. Tumor imaging for clinical purposes (i.e. whole body FDG PET coregistered with whole body CT scan with IV contrast) and assessment of clinical response will be performed at least 5 days before C11-AMT PET scan. The serum  $\beta$ -hCG pregnancy test should be done within 14 days of C11-AMT scan and within 72 hours of initiating pembrolizumab treatment in women of childbearing potential. Brain MRI should be obtained within 8 weeks of C11-AMT PET imaging.

A window of  $\pm 2$  days will apply to all study visits including treatment visits. CBC w/diff, chemistry, and LFTs on day 1, cycle 1 of pembrolizumab will be repeated only if  $>7$  days have elapsed between screening laboratory tests and day 1.

Study-related treatment with pembrolizumab is 12 weeks (or earlier if patient progresses). The end of study treatment visit should occur under the following circumstances: (1) Patients permanently stop pembrolizumab for disease progression or investigator/patient preference. Such visits should be performed 30 days ( $\pm 7$  days) after the last dose of pembrolizumab. (2) Patients who have an ongoing  $\geq$  grade 2 or serious AE (SAE) should be followed until the event is resolved or deemed irreversible by the investigator. (3) Patients who are still experiencing clinical benefit (partial response, complete response, disease stability) after 12 weeks of pembrolizumab treatment will discuss with their clinician to continue pembrolizumab as per standard of care (i.e., off study-related treatment but follow up will continue as specified in Section 6.4), especially if they are tolerating treatment well (i.e., are experiencing no ongoing SAEs), wish to continue receiving pembrolizumab.

The first long-term follow-up visit is defined as 90 days ( $\pm 15$  days) after the last dose of on-study treatment. Serious adverse events (SAEs; or follow-up to any SAEs) that occur within 90 days of the end of pembrolizumab (or prior to start of new anti-cancer therapy, whichever is earlier) or any grade of Events of Clinical Interest (see section 7.3 that occur within 90 days of the end of pembrolizumab or 30 days after the initiation of a new anti-cancer therapy (whichever is earlier) must be recorded. Subsequent follow-up visits, defined as every 3 months (90 days) thereafter ( $\pm 15$  days) for up to 3 years or until death (whichever is first) may be conducted via telephone or

chart review. These follow up visits will be limited to history of any subsequent cancer treatments, an assessment of any SAE's considered to be possibly or probably related to pembrolizumab treatment until resolution, date of disease progression on pembrolizumab, and survival status.

Complete history at baseline, physical exam to include height (baseline only), weight and vital signs (BP, respiratory rate, and temperature).

Hgb, ANC, and platelets

Serum chemistries and electrolytes to include sodium, potassium, bicarbonate, chloride, LDH, BUN, serum creatinine, glucose, calcium, magnesium, total protein, albumin.

LFTs include total bilirubin, AST and ALT.

Thyroid panel includes TSH, T3 and free T4. This test should be performed at screening, D1 of cycle 3, and at the end of treatment.

A urine or serum pregnancy test ( $\beta$ -hCG) is required for all women of childbearing potential at screening within 14 days of the C11-AMT scan and 72 hours before the first dose of pembrolizumab.

Optimal radiographic tumor imaging for baseline clinical purposes includes whole body CT scan (chest, abdomen, and pelvis; add neck, if clinically necessary) with IV contrast coregistered with whole body F-fluorodeoxyglucose (FDG) PET. Brain MRI (or head CT with IV contrast, if MRI is not applicable) is not required at screening if it has been performed within 8 weeks from C11-AMT imaging and was negative for parenchymal brain metastases or leptomeningeal disease. Tumor imaging requirements at screening may be adjusted to take into account the type of tumor imaging done before study enrollment (i.e. whole-body CT scan –chest, abdomen, and pelvis; add neck, if applicable- with IV contrast alone or whole body FDG PET coregistered with CT scan without IV contrast) in relation with timing of C11-AMT PET imaging or pembrolizumab initiation. See section 4.1 for details. Scans for disease assessment will be done at baseline and week 12 (or earlier if patient progresses). If patients continue to have clinical benefit (complete response, partial response, disease stability) after 12 months from pembrolizumab treatment they can continue to be imaged per standard of care.

CT scan of the chest abdomen and pelvis (add neck, if applicable) will be performed twice at baseline: (A) coregistered with FDG PET; in this case IV contrast will be administered, (B) coregistered with C11-AMT PET; in this case no IV contrast will be administered with CT and radiology report will be issued for clinical assessment of tumor burden.

Limited (i.e. not whole body; at least 1 bed position) scan will be performed as described in sections 4.1.1 and 4.1.2 and before fresh tumor biopsy.

Observer-rated toxicity will be assessed using the NCI-CTCAE v4.03

Fresh biopsy is mandatory for all patients (except for patients with metastatic lung disease in which case it is optional) and will be performed during the pre-treatment period at least 24 hours following C11-AMT PET imaging and before pembrolizumab. Further details to be provided in a study manual.

## 6.2 Pre-Study Assessments

### 6.2.1 Screening Period

Clinical evaluation: complete history; physical exam to include height (baseline only) and weight; ECOG performance status (see Appendix A ECOG Performance Status)

Laboratory studies:

- **Pregnancy Test:** A urine or serum pregnancy test ( $\beta$ -hCG) is required for all women of childbearing potential at screening within 14 days prior to C11-AMT PET imaging
- **Hematology:** Hgb, absolute lymphocyte count, and platelet count
- **CBC w/differential**
- **Serum Chemistries:** These include the following parameters: sodium, potassium, bicarbonate, chloride, LDH, BUN, creatinine, glucose, calcium, magnesium, albumin, and total protein (or calculate creatinine clearance via Cockcroft-Gault (see Appendix B Cockcroft-Gault Formula and as noted in inclusion criterion #9)
- **LFTs:** These include total bilirubin, AST (SGOT), ALT (SGPT)
- **INR and PT or PTT** (Note: Patient entering the study while receiving coumadin for anti-coagulation therapy or those who will initiate coumadin for anti-coagulation therapy should have their coagulation test performed per standard of care)
- **Thyroid Panel:** TSH, free T4 (prior to cycles 1 and 3)

Concomitant Medications: Review (see section 4.4)

Toxicity Assessment: Perform per NCI CTCAE v4.03

Tumor imaging for clinical purposes: Baseline tumor imaging for clinical purposes should include  $^{18}\text{F}$ -fluorodeoxy glucose (FDG PET) whole body co-registered with computed tomography (CT) of the neck, chest, abdomen and pelvis) with IV contrast and brain MRI.

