9. Has not received prior therapy with CTLA-4, PD-1/PD-L1 inhibitors, other co-stimulatory or co-inhibitory immune checkpoint antibody therapies (e.g. LAG3, TIM3, CD137, KIR3DL, CD70, and CD27) for distant metastatic melanoma. Patients who have received MAPK inhibitors are allowed on condition that they have recovered from adverse events to at most Grade 1 by CTCAE v4.03 and at least 15 days have elapsed between last dose of MAPK inhibitors and C11-AMT imaging. Patients who have previously received CTLA-4 inhibitors in the adjuvant setting are allowed to participate as long as they discontinued CTLA-4 treatment at least 30 days ago and meet criteria outlined in inclusion #14. Patients who have previously received adjuvant PD-1 inhibitors are excluded.
10. Demonstrate adequate organ function as defined in the table below; all screening labs to be obtained within 14 days prior to C11-AMT PET scan.

System	Laboratory Value
Hematological	
Hemoglobin (Hgb)	≥ 9 g/dL or ≥ 5.6 mmol/L without transfusion or EPO dependency (within 7 days of assessment of Hgb)
Absolute Neutrophil Count (ANC)	≥ 1,500/mm 
Platelets	≥ 100,000/mm 
Renal	
Serum Creatinine OR Measured or calculated creatinine clearance (GFR can also be used in place of creatinine or CrCl)	≤1.5 x ULN OR  ≥ 60 mL/min using the Cockcroft-Gault formula for subject with creatinine levels > 1.5 X institutional upper limits of normal (ULN)
Hepatic	
Serum Total Bilirubin	≤ 1.5 X ULN
Aspartate aminotransferase (AST)	≤ 2.5 X ULN OR < 5 X ULN for subjects with liver metastases

Alanine aminotransferase (ALT)	$\leq 2.5 \times \text{ULN}$ OR $< 5 \times \text{ULN}$ for subjects with liver metastases
Albumin	$\geq 2.5 \text{ mg/dL}$
Coagulation	
International Normalized Ratio (INR) or Prothrombin Time (PT)	$\leq 1.5 \times \text{ULN}$ , unless subject is receiving anticoagulant therapy as long as PT or PTT is within therapeutic range of intended use of anticoagulants
Activated Partial Thromboplastin Time (aPTT)	$\leq 1.5 \times \text{ULN}$ , unless subject is receiving anticoagulant therapy as long as PT or PTT is within therapeutic range of intended use of anticoagulants

11. Female subjects of childbearing potential should have a negative urine or serum pregnancy within 14 days prior to C11-AMT PET scan. If the urine test is positive or cannot be confirmed as negative, a serum pregnancy test will be required.

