12. Female subjects of childbearing potential must be willing to use adequate methods of contraception as outlined in Section 5.1.7 – Contraception for the course of the study through 120 days after the last dose of study medication. Subjects of childbearing potential are those who have not been surgically sterilized or have not been free from menses for > 1 year.

**NOTE:** Abstinence is acceptable if this is the usual lifestyle and preferred contraception for the subject.

Male subjects should agree to use an adequate method of contraception as outlined in Section 5.1.7- Contraception starting with the first dose of study therapy through 120 days after the last dose of study therapy.

**NOTE:** Abstinence is acceptable if this is the usual lifestyle and preferred contraception for the subject.

13. Patients who have received prior adjuvant high dose interferon are allowed to participate as long as the last injection was given at least 30 days prior to the C11-AMT PET scan and they have fully recovered from side effects (i.e., Grade  $\leq 1$  or permanent side effects that require hormone replacement therapy).
14. Patients on adjuvant ipilimumab are allowed to participate at least 30 days from drug discontinuation as long as they have at most Grade 1 adverse events (or grade 2 if they have to received hormone replacement therapy for their otherwise grade 1 ipilimumab-induced autoimmune endocrinopathies).

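### Inclusion criterion 10 prints the albumin limit as 2.5 mg/dL (0.0025 g/dL), so as written it cannot exclude any patient

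*Combined protocol and SAP*

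**What the plan says.** Section 3.1, inclusion criterion 10, reads "10. Demonstrate adequate organ function as defined in the table below". The table gives limits for blood counts, renal function, liver function and coagulation. Albumin is in the hepatic block, with a lower limit of 2.5 mg/dL. Hemoglobin, in the same table, is limited in grams: "≥ 9 g/dL or ≥ 5.6 mmol/L". The renal block holds the creatinine-clearance rule: "≥ 60 mL/min using the Cockcroft-Gault formula for subject with creatinine levels".

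Albumin is measured at screening (Section 6.2.1), on Day 1 of Cycles 1 to 4 (Sections 6.3.1 and 6.3.2) and at end of treatment (Section 6.3.3). It is also listed in footnote 7 of the Time and Events Table. None of these places gives a unit or a limit, so criterion 10 is the only statement of the albumin threshold.

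The serum chemistry item in Section 6.2.1 allows creatinine clearance to be calculated and directs the reader as follows: "see Appendix B Cockcroft-Gault Formula and as noted in inclusion criterion #9". Criterion 9 in the current Section 3.1 begins "9. Has not received prior therapy with CTLA-4, PD-1/PD-L1 inhibitors".

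**The concern.** A threshold in an eligibility table should separate patients who qualify from those who do not. If the printed limit lies far below any value a laboratory could report, the row does no work: albumin is measured, compared with the limit, and always passes.

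What is at stake is uniform eligibility. The trial admits patients from affiliate sites, and the same result could be judged in two ways. Read literally, the row is satisfied. A reader who assumes that grams were meant and applies 2.5 g/dL might find that it is not. The second reader has no written basis for that decision in criterion 10.

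The cross-reference in Section 6.2.1 is a smaller matter. It sends the reader to a criterion that contains no laboratory limit.

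**Working it through.** **Albumin limit**

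Inputs: the limit of 2.5 mg/dL (Section 3.1, criterion 10) and the conversion 1 g/dL = 1,000 mg/dL. The albumin range is an assumption, because the documents give none. It is set wide, at 0.5 to 5 g/dL.

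1. Limit in grams: 2.5 / 1,000 = 0.0025 g/dL, or 0.025 g/L.
2. Ratio of a value to the limit: (value in g/dL × 1,000) / 2.5.

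| Assumed albumin (g/dL) | In mg/dL | Multiple of the printed limit | Passes as written |
|---|---|---|---|
| 0.5 | 500 | 200 | yes |
| 1.5 | 1,500 | 600 | yes |
| 2.0 | 2,000 | 800 | yes |
| 2.4 | 2,400 | 960 | yes |
| 3.5 | 3,500 | 1,400 | yes |
| 5.0 | 5,000 | 2,000 | yes |

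3. The result does not depend on the range chosen. Any value of 0.0025 g/dL or more passes.
4. Two readings of one patient: at 2.0 g/dL the printed limit is met, since 2,000 mg/dL exceeds 2.5 mg/dL. A reader who substitutes 2.5 g/dL finds it not met, since 2.0 is below 2.5. This shows that the readings diverge. It does not establish which limit was intended.

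**Cross-reference**

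1. Section 6.2.1 cites criterion 9 for creatinine clearance.
2. Current criterion 9 concerns prior therapy. The Cockcroft-Gault rule is in the table under criterion 10.
3. Check that the current numbering is sound: criterion 9 requires patients with adjuvant CTLA-4 treatment to "meet criteria outlined in inclusion #14", and that criterion reads "14. Patients on adjuvant ipilimumab are allowed to participate at least 30 days from drug discontinuation". The list is therefore consistent with itself, and the reference in Section 6.2.1 is one number too low.
4. The Amendment 2 summary of changes refers to the screening-laboratory criterion as number 9. That may explain the slip, but it describes superseded text and is not the evidence for it.

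**The case against.** The strongest case against is about consequence. Readers used to albumin in g/dL would probably notice the unit and read the row as grams. Eligibility is also not settled by one person: under footnote 1 of the Time and Events Table and Section 9.3, the coordinating site's study coordinator reviews it, and the Principal Investigator and Multicenter Project Manager sign off, with source documents due at least 4 days before the C11-AMT scan. The other limits in the table still apply. All of this stands and makes the practical effect likely small, but none of it corrects the text.

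Three stronger readings are tempting, and the documents do not support them.

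- A reader might infer that a site declining a patient at 2.0 g/dL would breach the protocol, because Section 9.5.2 forbids eligibility exceptions. Exclusion criterion 14 allows the treating investigator to exclude for a laboratory abnormality on stated grounds, and declining a patient on that basis is not an exception. Section 9.5.2 also appears under a heading for institutions relying on the coordinating university's IRB.
- A reader might infer that the limit is wrong by exactly a factor of 1,000. A unit slip is likely, and hemoglobin in g/dL in the same table points that way, but no document states the intended value.
- A reader might infer that patients with very low albumin will be enrolled, biopsied and treated as a result. The documents give no figure for how many screened patients have low albumin, and discretion under exclusion criterion 14 remains.

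It is also fair to object that the two slips are unrelated. The reference in Section 6.2.1 concerns creatinine clearance, does not cause the albumin problem, and is unlikely to mislead, since criterion 10 follows criterion 9 directly and is the one with the Cockcroft-Gault rule.

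**Conclusion.** The point holds. As printed, the albumin row of criterion 10 excludes nobody, and no other section supplies a limit or unit that would correct it. Low albumin is therefore governed only by discretion under exclusion criterion 14, and two careful readers can reach different decisions on the same patient. The inability to exclude follows from unit conversion and the premise that no patient has albumin below 0.0025 g/dL; the 200- to 2,000-fold figure rests on the assumed range.

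The matter is worth correcting because the row is an operative eligibility threshold. Its reach is limited to eligibility checking: nothing in the endpoint definitions, the sample size of 27 (23 evaluable) or the analyses in Section 8 uses albumin. The reference to criterion 9 in Section 6.2.1 is a clerical error.

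**What to change.** The sponsor should confirm the intended albumin value and unit, restate the row in criterion 10 accordingly, and make the eligibility checklist agree with it. The number should not be inferred from the present text. In the same amendment, the creatinine-clearance reference in Section 6.2.1 should be changed from inclusion criterion 9 to inclusion criterion 10.

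The drafting cost is one table row, one cross-reference and one checklist line. The downside is that, once the limit operates, a patient with very low albumin might be screened out. The documents do not allow an estimate of how often. No statistical section needs to change.
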